4 INVESTIGATIONAL PLAN

4.1 Study Design

This is a single-center, prospective, open label, feasibility study in healthy adult participants. Eligible participants who have signed an informed consent will be enrolled in the study. The participant will be assigned a unique ID number. After obtaining relevant demographic information, testing will ensue.

Baseline vital sign measurement (heart rate, temperature, blood pressure, respiratory rate) will be obtained. The participant will then undergo continuous MRI of the brain to include sequences that enable thermography. Baseline imaging sequences will take approximately 30 minutes. The investigator or designee will turn on the VCool System, while the VCool remains outside of the MRI suite, for up to two hours or until the target temperature of 35.5°C is reached. Body temperature will be continuously measured using a MRI compatible thermometer. During the cooling period and once endpoint is reached the participant will undergo repeated MRI with thermography. Once study endpoint is reached, the participant will be taken off of VCool and MRI thermography. If the target core body temperature is reached before 2 hours, the participant will be monitored until two hours are completed to determine if the VCool System can maintain the participant's core body temperature between 35°C and 36°C for one hour.

During the study, the participants will have their temperature monitored and will be assessed for shivering and adverse events.

Study participation is one visit lasting approximately 4 hours.

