5 STUDY ENDPOINTS

5.1 Primary Endpoints

1. To confirm the VCool System can lower core body temperature to 35.5°C within 2 hours.
2. To identify whether cooling with the VCool System results in a gradient between brain and core body temperature.
3. To confirm the VCool System can maintain a core body temperature between 35°C and 36°C for one hour after cooling.

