6 STUDY POPULATION

6.1 Inclusion Criteria

Participants are eligible for enrollment if all the inclusion criteria are met:

1. Male or female ages 18 to 55

2. An Institutional Review Board (IRB) approved informed consent is signed and dated prior to any study-related activities
3. Core body temperature between 36.8°C and 37.5°C
4. Have the ability to understand the requirements of the study and are willing to comply with all study procedures
5. In the opinion of the Investigator, are able to participate in the study

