2. If temperature continues to fall below 35°C after 2 minutes, cover patient with electric blanket that has been pre heated on standby. Keep blanket on until temperature gets back to 35°C.

Assess for shivering every 10 minutes using the BSAS. Record the results and time. The BSAS is recorded throughout the study.

Bedside Shivering Assessment Scale

0	None
1	Mild: Shivering localized to neck/thorax
2	Moderate: Intermittent involvement of the upper extremities and/or thorax
3	Severe: Generalized shivering or sustained upper and/or lower extremity shivering

The flow can be increased to 40 liters per minute after 10 minutes

Record any VCool System adjustments to flow rate or temperature and record the new flow rate and temperature and time of adjustment. Record the reason for the adjustment.

Assess the participant for adverse events (AEs) throughout the study

If the participant has a nosebleed, discontinue the study and note the time.

Monitor patient at first sign of shivering

- If **Mild**, cover patient with regular blanket.
- If **Moderate or severe** – discontinue cooling treatment.

Continue to record the temperature until either temperature sensor reaches 35.5°C or the VCool System has been used for 2 hours. Note the time the target temperature was achieved.

If the participant's core body temperature does not reach 35.5°C in 2 hours, the study is concluded

- Remove the nasal cannula from the participant and dispose of it properly
- Monitor the participant's core body temperature until it returns to baseline. Blankets can be applied to help with warming.
- Remove the axillary thermometer

If the participant's core body temperature reaches 35.5°C, proceed to the next steps

Maintain the target temperature of 35.0°C to 36.0°C for 1 hour:

Adjust flow rate by 5 liters per minute from baseline every 2 minutes

- If temperature falls below 35°C., reduce flow rate by 5 liters per minute every 2 minutes until temperature rises back to 35°C
- If temperature rises above 36°C, increase flowrate 5 liters per minute every 2 minutes until temp falls below 36°C

Remove the nasal cannula and the air delivery tube and dispose of them properly

Once out of the MRI suite, record the patient temperature (°C) using the 3M SpotOn® zero-heat-flux forehead sensor, the Braun ThermoScan 7 tympanic sensor

Monitor the participant's core body temperature until it returns to baseline. Blankets can be applied to help with warming.

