12 DATA ANALYSIS

12.1 Primary Analysis

The time and flow rate that is required to reduce and maintain each participant's core temperature to 35.5°C from measured baseline temperature will be calculated. The total number of participants who reach the target temperature in 2 hours or less will be calculated.

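### Primary endpoint 3 sets out to confirm that VCool maintains 35–36°C for an hour, but with no device-off reference an in-band hour is also what unaided rewarming of 0.5°C/h or less would give

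*Protocol*

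**What the plan says.** Section 5.1 lists as its third primary endpoint "To confirm the VCool System can maintain a core body temperature between 35°C and 36°C for one hour after cooling"; the synopsis carries the same aim. Section 7.6.3 fixes the start of the hour: "Continue to record the temperature until either temperature sensor reaches 35.5°C or the VCool System has been used for 2 hours". It then instructs staff: "Maintain the target temperature of 35.0°C to 36.0°C for 1 hour". During that hour the device runs. Besides a general line on adjusting flow every 2 minutes, the rules that give a direction lower the flow below 35°C and raise it above 36°C. After the cannula is removed the instruction is: "Monitor the participant's core body temperature until it returns to baseline. Blankets can be applied to help with warming".

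On design, Section 4.1 states: "This is a single-center, prospective, open label, feasibility study in healthy adult participants". There is no control arm and no device-off reference period.

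On analysis, Section 12.1 states: "The time and flow rate that is required to reduce and maintain each participant's core temperature to 35.5°C from measured baseline temperature will be calculated". It also counts participants who reach the target in 2 hours or less. It names no reference for unaided rewarming.

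Section 4.1 also says: "Once study endpoint is reached, the participant will be taken off of VCool and MRI thermography". That does not fit with Section 7.6.3, where the device runs through the maintenance hour.

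**The concern.** The endpoint credits the device with an outcome that has two possible causes: cooling that offsets rewarming, or rewarming too slow to leave the band within an hour. To tell them apart one needs to know what the participant's temperature would do with the device off, and the plan provides no such figure.

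The flow record does not supply it. While temperature is inside the band neither directional flow rule is triggered, so a participant who stays in band may show no response to a change in flow. The flow that happened to be running could still be listed under Section 12.1 as the flow required to maintain temperature.

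Two things are at stake. One is the wording of a primary conclusion. The other is the use named in Section 2.2, where cooling response as a function of flow and time is to feed automated cooling models and a control algorithm. A holding flow is informative there only if the drift without it is known.

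**Working it through.** The protocol states no rewarming rate, success threshold or sample-size derivation for this endpoint, so there is no figure of the plan's own to reproduce.

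**Inputs.** Band 35.0–36.0°C and duration 1 h (Section 5.1). Start at 35.5°C on either sensor (Section 7.6.3). Baseline from Section 6.1: "Core body temperature between 36.8°C and 37.5°C". Baseline imaging of about 30 minutes and a visit of about 4 hours (Section 4.1).

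**Step 1: tolerated unaided rise, linear.** (upper limit − start) / duration = (36.0 − 35.5) / 1 h = 0.5°C/h. With rate r, temperature at 1 h is 35.5 + r, and 36.0°C is reached after 0.5/r hours.

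| Unaided rise (assumed), °C/h | Temperature at 1 h, °C | Reaches 36.0°C after, h | In band for the hour with no device effect |
|---|---|---|---|
| 0.2 | 35.7 | 2.50 | yes |
| 0.3 | 35.8 | 1.67 | yes |
| 0.5 | 36.0 | 1.00 | yes (at the limit) |
| 0.7 | 36.2 | 0.71 | no |
| 1.0 | 36.5 | 0.50 | no |
| 1.5 | 37.0 | 0.33 | no |

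**Step 2: rewarming that slows towards baseline B.** Let T(t) = B − (B − 35.5)·exp(−kt). Staying at or below 36.0°C at 1 h requires k ≤ ln[(B − 35.5)/(B − 36.0)], and the initial rate is k·(B − 35.5).
- B = 36.8: k = ln(1.3/0.8) = 0.486 per hour; initial rate 0.486 × 1.3 = 0.63°C/h.
- B = 37.5: k = ln(2.0/1.5) = 0.288 per hour; initial rate 0.288 × 2.0 = 0.58°C/h.

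The tolerated rate is thus 0.5 to about 0.6°C/h, depending on the shape of the curve.

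**Step 3: dependence on start and duration.** A start at 35.0°C tolerates 1.0°C/h and a start at 35.8°C tolerates 0.2°C/h. This matters because the trigger is either sensor. If the 2-hour limit in Section 4.1 cut the window to 30 or 15 minutes, the tolerated rate would be 0.5/0.5 = 1.0 or 0.5/0.25 = 2.0°C/h.

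**Step 4: illustration only.** Suppose unaided rates are normal with SD 0.2°C/h (assumed). The proportion at or below 0.5°C/h is Φ((0.5 − mean)/0.2). Means of 0.3, 0.5, 0.7 and 1.0°C/h give 84%, 50%, 16% and 0.6%, or about 8.4, 5.0, 1.6 and 0.1 of 10 participants. The answer depends almost wholly on a mean that the protocol does not give.

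**Step 5: what the visit length suggests.** 4 − 0.5 (imaging) − 1 (hold) = 2.5 h for induction plus rewarming. At 0.5°C/h, return from 35.5°C takes 1.3/0.5 = 2.6 h to 2.0/0.5 = 4.0 h. Even from 36.0°C it takes 0.8/0.5 = 1.6 h to 1.5/0.5 = 3.0 h. A visit of about 4 hours that includes monitoring back to baseline therefore points weakly towards faster rewarming. It does not settle the matter, since the duration is approximate and blankets are allowed.

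**Step 6: whether the reference data will exist.** Section 7.6.3 asks for 2-minute recording, but ties continued recording to reaching 35.5°C or 2 hours of use. After cannula removal it asks for monitoring, without set recording times. It also changes sensor: forehead and tympanic readings are taken once the participant is out of the MRI suite.

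**The case against.** The strongest reply is that this is a 10-person feasibility study gathering preliminary data, with no hypothesis test. Device use in the hour is documented, since each adjustment is logged with time and reason, and slope estimates could be left to a statistical analysis plan. This stands as far as severity goes. It does not remove the point, because the protocol itself fixes the word *confirm*, and a later analysis plan cannot recover readings that were never taken.

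A reader might infer more than the documents support, in four ways:

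- *That a maintenance count will be reported as proof.* Section 12.1 counts only participants who reach the target. No maintenance count, and no rule that a single out-of-band reading is a failure, is stated.
- *That the endpoint rewards a weak device over a strong one*, because continued cooling would take a participant below 35°C. Section 7.6.3 reduces flow below 35°C, and a two-sided band ought to count overcooling against maintenance.
- *That most in-band hours will be passive.* No rewarming rate is given, and the visit length leans the other way.
- *That the difference between device-off and device-on slopes would settle attribution for each participant.* The device-off slope follows a cooled hour and may span the exit from the MRI suite with a change of sensor. Blankets are possible on both sides, since Section 7.6.3 also provides one for mild shivering during cooling. The slope is useful context and an imperfect counterfactual.

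**Conclusion.** The point holds in a limited, conditional form. As worded, endpoint 3 cannot separate maintenance by the device from unaided rewarming of 0.5°C/h or less (up to about 0.6°C/h if rewarming slows towards baseline). That figure rests on a start at exactly 35.5°C, a full hour and no sensor noise. Clearly above that range, an in-band hour is evidence of a device effect. Which case applies cannot be decided from the protocol, so the size of the problem is unknown.

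The fault lies in the confirmatory wording and the missing device-off record. Collecting the hour of data is sound. The point holds with the device running as in Section 7.6.3. If Section 4.1 is read literally, the device would be off in the hour credited to it. That contradiction is a separate matter and must be resolved in its own right.

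**What to change.** 1. **Section 7.6.3.** Extend the existing 2-minute temperature recording, on the same sensor used in the maintenance hour, from cannula removal until return to baseline, and make plain that it also covers the hour itself. Note the time of any blanket, both during the hour and after removal.
2. **Section 12.1.** For each participant, report side by side and descriptively: the in-band result, the device-on slope with the flow in use, and the device-off slope from readings before any blanket. No attribution threshold is needed, and the conclusion should not rest on the slope difference.
3. **Section 5.1 and synopsis.** Word the endpoint as describing core temperature during the hour after cooling, in place of confirming maintenance by the device.
4. **Limitations to state.** The device-off slope follows a cooled hour, may span the exit from the MRI suite, and may be short or missing where a blanket is applied at once.
5. **Separately,** reconcile Sections 4.1 and 7.6.3 on whether the device runs in the maintenance hour, and how long that hour lasts given the 2-hour limit in Section 4.1.

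Cost: changes to protocol and CRF wording, and a little more recording of temperatures that staff already monitor. There are no extra participants and no change to care. The downside for the sponsor is a less favourable statement about maintenance.

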5.2 Secondary Endpoint

4. To assess the shivering experienced by participants based on the 4-point Bedside Shivering Assessment Scale (BSAS).

5.3 Safety Considerations

All treatment emergent adverse events (TEAEs) reported by participants will be tabulated.

Each adverse event (AE) will be evaluated by the Investigator in terms of seriousness, severity (mild, moderate, severe) and relationship (not related, possibly related, probably related, definitely related) to the study device.

6 STUDY POPULATION

6.1 Inclusion Criteria

Participants are eligible for enrollment if all the inclusion criteria are met:

1. Male or female ages 18 to 55

2. An Institutional Review Board (IRB) approved informed consent is signed and dated prior to any study-related activities
3. Core body temperature between 36.8°C and 37.5°C
4. Have the ability to understand the requirements of the study and are willing to comply with all study procedures
5. In the opinion of the Investigator, are able to participate in the study

6.2 Exclusion Criteria

Participants are not eligible for enrollment if any of the exclusion criteria apply:

1. History of cardiovascular, respiratory, or metabolic disorder.
2. Any contraindication to undergoing Magnetic Resonance Imaging (MRI)
3. Pregnant
4. Severe peripheral vascular disease
5. History of Raynaud's disease
6. Currently experiencing a respiratory infection
7. Chronic rhinosinusitis
8. History of sickle cell disease
9. History of cold agglutinin disease
10. History of cryoglobulinemia
11. Known deviated septum or nasal deformity
12. History of nosebleeds or a nosebleed within past 24 hours
13. Use of antipyretics or other medications affecting body temperature within the past 24 hours

6.3 Study Duration

Each participant's involvement in the study will be one study visit lasting approximately 4 hours. No follow-up or subsequent participant involvement is required. Study enrollment is expected to be completed within 8 weeks.

7 STUDY PROCEDURES

7.1 Pre-screening

Potential participants will be pre-screened by a designated member of the study team to determine if the potential participant meets any of the exclusionary criteria based on medical history. If the participant is determined to be potentially eligible for participation, they will be scheduled for a screening visit at the study site.

7.2 Screening

7.2.1 *Informed Consent*

Study staff trained in basic human research subjects protection will explain the study protocol, procedures, and objectives to the volunteer and obtain written informed consent for participation in the study prior to performing any study procedures, in accordance with the requirements outlined in the Code of Federal Regulations (CFR) Title 45, Part 46 and Title 21, Part 50. This will be done by reviewing all the information contained in the informed consent form (ICF), allowing the volunteer ample time to review the form, ask questions, and have their questions answered to the satisfaction of the volunteer. The ICF will be presented to the volunteer in a language that is fully comprehensible to them.

Volunteers wishing to participate will be asked to sign and date the ICF and will be provided with a copy for their records. The original will be maintained with the participant's study records.

7.3 Study Enrollment

7.3.1 *Participant Identification*

If the volunteer is willing to participate in the study and has signed and dated the ICF, they will be assigned a unique ID number. The ID number is a 2-digit number assigned sequentially (i.e., 01, 02, 03). The ID number will be written on each page of the CRF, and all other documents related to the participant.

The site will maintain a screening and enrollment log for participant identification, to which all consented participants will be added. A participant is considered enrolled when they have signed the ICF. If during the screening process a participant fails to fulfill any of the eligibility criteria, this will be documented, and the participant will be classified as a screen failure. Volunteers will continue to be screened until 10 participants have completed the study.

The Principal Investigator (PI) or designee at each site will maintain a master log that will correlate each participant ID number to the participant's name. The log will remain with the PI and will be confidential.

7.3.2 *Participant Stipend*

Participants will be issued a stipend of 200\$ for their participation in the study.

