1 PROTOCOL SYNOPSIS

Protocol Title:	Feasibility Study for VCool Intranasal Cooling System in Healthy Volunteers
Protocol Number:	00080424
Version:	2.0
Date:	01 August 2024
Development Phase:	Pilot Study
Sponsor:	NeuroIntact, Inc. [name]
Study Objective:	The objective of this study is to evaluate the performance and safety of the VCool Intranasal Cooling System in healthy adult volunteers. The study is designed to gather preliminary data regarding air flow rates and time required to reduce core body temperature to 35.5°C and maintain the temperature between 35°C and 36°C for one hour after cooling.
Number of Sites / Number of Participants:	The study will be conducted at one site in Maryland. A total of 10 participants need to complete the study.
Primary Endpoints:	
1. To confirm the VCool System can lower core body temperature to 35.5°C within 2 hours.2. To confirm the VCool System can maintain a core body temperature between 35°C and 36°C for one hour after cooling.3. To demonstrate the differential impact of VCOOL system between core body and brain temperature
Secondary Endpoint:	
1. To assess the shivering experienced by participants based on the 4-point Bedside Shivering Assessment Scale (BSAS).
Safety Evaluation:	All treatment emergent adverse events (TEAEs) reported by participants will be tabulated. Each adverse event (AE) will be evaluated by the Investigator in terms of seriousness, severity (mild, moderate, severe) and relationship (not related, possibly related, probably related, definitely related) to the study device.
Study Design:	This is a single-center, prospective, open label, feasibility study in healthy adult participants. Participants will be monitored for up to 2 hours while using the VCool System to determine if the target temperature of 35.5°C is reached. If the target core body temperature is reached within 2 hours, the participant will be monitored for an additional hour to determine if the VCool System can maintain the participant's core body temperature between 35°C and 36°C for one hour.

	During the study, the participants will have their blood pressure and temperature monitored and will be assessed for shivering and adverse events.
Study Duration:	The overall study participation for each participant will be one visit lasting approximately 4 hours. Study enrollment is anticipated to be completed within two weeks.

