2.3 Risk and Benefit Assessment

2.3.1 Potential Risks

The only known study-related risk is the use of a nasal cannula to deliver cold air to the participant. The potential risks associated with this delivery are:

Nosebleed

Shivering

Irritation of the nasal passages

Skin irritation at the site of the cannula

Nasal congestion

Over cooling

Participants will be de-identified using a study specific number at the time of enrollment. All Case Report Forms (CRFs) will be labeled with the de-identified participant identification (ID) number. No identifiable participant identification information will be provided to NeuroIntact.

Information collected for this study is confidential. However, officials of the Food and Drug Administration (FDA) or other regulatory agencies may research records during the ordinary course of carrying out their functions. A Sponsor representative may also inspect the research records to make certain the study data is accurate. The Investigator, regulatory agencies, and the Sponsor will protect the confidentiality of the records.

2.3.2 *Risk Mitigation*

The protocol has been designed to minimize the risks to study participants enrolled in the study. In general:

- Prior to study enrollment the Investigator must ensure the participant meets the inclusion/exclusion criteria
- Each participant will be fully informed about the conditions of study participation, and the risks and potential benefits of the study procedure and asked to provide an executed Informed Consent prior to being enrolled in the study
- Institutional Review Board (IRB) review and approval of the study protocol, Informed Consent Form, and any other participant-facing documents will be obtained prior to study initiation.
- The participant's core temperature will be continuously monitored with direction to adjust the VCool if the core temperature is $<35^{\circ}\text{C}$ for a sustained period of 5 minutes, to mitigate overcooling of the participant
- If the participant develops a nosebleed, the VCool will be stopped
- Participants will be assessed for shivering and if severe according to the Bedside Shivering Assessment Scale, the VCool flow and temperature will be adjusted

2.3.3 *Potential Benefits*

The information obtained in this study will not benefit the study participants directly but may aid future patients requiring cooling of body temperature.

2.4 *Study Rationale*

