4.3 Participant Enrollment

Participants will be screened for inclusion in the study to ensure that 10 participants complete the study.

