12.3 Populations for Analysis

The study population will consist of 10 healthy volunteers who have signed the ICF and who meet all the inclusion criteria and none of the exclusion criteria.

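### Section 12.3 fixes the analysis population at 10 by consent and eligibility while recruitment runs to 10 completers, so a clear non-completion followed by a further recruit leaves the denominator unsettled

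*Protocol*

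**What the plan says.** Three places in the protocol set recruitment by completion. The synopsis says "A total of 10 participants need to complete the study", section 4.3 says "Participants will be screened for inclusion in the study to ensure that 10 participants complete the study", and section 7.3.1 says "Volunteers will continue to be screened until 10 participants have completed the study".

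Section 12.3 sets the population for analysis by other criteria, with the same number: "The study population will consist of 10 healthy volunteers who have signed the ICF" and who satisfy all inclusion and no exclusion criteria. Completion is not mentioned.

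The protocol expects some eligible participants to stop early. Section 7.6.3 says "If the participant has a nosebleed, discontinue the study and note the time". Section 8 allows for withdrawal of consent, withdrawal for an adverse event, and a decision by the investigator. Section 20.2 requires a reason whenever someone does not complete.

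For severe shivering the protocol gives two responses. Under section 2.3.2 "the VCool flow and temperature will be adjusted"; under section 7.6.3 cooling is ended for moderate or severe shivering.

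Section 12.1 plans to count the participants who reach the target temperature in 2 hours or less. It names no denominator.

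**The concern.** The two uses of 10 describe different groups. A participant who is eligible, is cooled and then has a nosebleed meets the 12.3 criteria but is hard to call a completer. Once another volunteer is recruited, 11 people meet the 12.3 criteria, and its stated number can be kept only by leaving one out. Because recruitment is counted in completers, the stopped participant is the natural one to omit.

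That omission would not be neutral. Nosebleed and shivering are listed device risks, and shivering is the secondary endpoint, so leaving out those who stop selects on how well the device was tolerated. What is at stake is how primary endpoint 1 is read: 8 participants reaching target means one thing out of 10 and another out of 12. If the choice is left open, it may be made after the results are known.

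**Working it through.** **The plan's figure.** The 10 is not derived from any power or precision calculation, so there is nothing to reproduce. A pilot study need not have such a derivation, and the number itself is not challenged.

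**Count of people meeting 12.3.** Let s be the number of eligible participants who sign consent but do not complete. Screen failures do not enter, because section 7.4 takes them no further and they fail 12.3 anyway. The number meeting 12.3 when recruitment ends is 10 + s, which equals 10 only if s = 0.

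**How often s > 0.** The protocol gives no stop rate. For an assumed independent probability d of clear non-completion, the chance of at least one among the first 10 is 1 − (1 − d)^10, and the expected number needed for 10 completers is 10/(1 − d).

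| d (assumed) | Chance of at least one stop | Expected number needed |
|---|---|---|
| 5% | 1 − 0.95^10 = 40.1% | 10.5 |
| 10% | 1 − 0.90^10 = 65.1% | 11.1 |
| 20% | 1 − 0.80^10 = 89.3% | 12.5 |

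**Effect on the 12.1 result.** Let x be the number of the 10 completers who reach 35.5°C within 2 hours, k the number stopped before target and m the number stopped after it. A stop after target is possible because of the maintenance period: "If the target core body temperature is reached within 2 hours, the participant will be monitored for an additional hour". A participant who misses the target at 2 hours is taken as a completer, since section 7.6.3 treats the study as finished for that person. Then:

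- completers only: x/10
- all started: (x + m)/(10 + k + m)

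With x = 8 (all counts assumed):

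| k | m | Completers only | All started |
|---|---|---|---|
| 1 | 0 | 8/10 = 80% | 8/11 = 72.7% |
| 2 | 0 | 8/10 = 80% | 8/12 = 66.7% |
| 2 | 1 | 8/10 = 80% | 9/13 = 69.2% |
| 0 | 3 | 8/10 = 80% | 11/13 = 84.6% |

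**Direction.** x/10 exceeds (x + m)/(10 + k + m) when x(k + m) > 10m, that is, when m/(k + m) < x/10. The completers-only figure is too high unless a large share of the stops come after target. The last row shows the reversal.

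**Precision.** Exact (Clopper-Pearson) 95% intervals are 44.4–97.5% for 8/10, 34.9–90.1% for 8/12 and 54.6–98.1% for 11/13. They overlap heavily, so the effect is a shift in a point estimate.

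**The case against.** The strongest reply is that no rule restricts the analysis to completers. Sections 4.3 and 7.3.1 say when screening ends, and a recruitment rule may properly differ from an analysis set. Read without the number, the 12.3 criteria keep a stopped participant in, and the 10 may be only the planned size carried over. This stands in part: a reader might infer that the protocol prescribes a completers-only analysis, and it does not. But the number is written into the definition, and after one clear non-completion and a further recruit the number and the criteria cannot both hold.

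A reader might also infer that the two rules agree only if no cooled participant is ever stopped. The documents do not support that either. Section 7.6.3 ends cooling for shivering without saying that participation ends, so such a participant might still count as completed. Conversely, an eligible participant who withdraws before cooling also breaks the match.

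It is also fair to say that 12.1 plans a count with no threshold or test, and that about 10 participants can be listed one by one. That limits the consequence. Nor would adverse events be lost: sections 5.3, 10 and 12.2 have them recorded and tabulated, and section 20.2 requires a case report form for everyone who signs consent.

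Finally, much of the detail belongs in a statistical analysis plan: the denominators for maintenance, the set for the brain–core comparison ("To identify whether cooling with the VCool System results in a gradient between brain and core body temperature") and the definition of the safety population named in section 10.1. That is accepted, and none of it is raised here. The clash between 12.3 and the recruitment rule is different, because the protocol itself states both sides.

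**Conclusion.** The point holds in a limited form and is minor. Section 12.3 and the recruitment rule agree while every eligible participant completes. After one clear non-completion and a further recruit, more than 10 people meet a definition fixed at 10, and the protocol does not say who is left out. If the stopped participant is dropped, the success proportion implied by the 12.1 count is usually too favourable: 80% against 67% in the example with two stopped before target. All stop rates and success counts are assumptions, the direction can reverse, and the intervals are wide. No pass/fail decision rests on it. The two responses to severe shivering contradict each other and matter here because they affect who is stopped; this review takes no position on which applies.

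**What to change.** - **12.3:** replace the fixed 10 with all eligible participants in whom VCool cooling was started. This also settles the case of a withdrawal before cooling.
- **7.3.1:** use 10 completed only to decide when recruitment ends. Define completed, and state whether a participant whose cooling was stopped for shivering counts.
- **12.1:** report the number reaching 35.5°C within 2 hours over all started. Count those stopped before target as not reaching it and those stopped after target as having reached it.
- **2.3.2 and 7.6.3:** reconcile the two passages on severe shivering.

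The cost is a short amendment. No added participants or procedures are needed, because section 20.2 already requires a case report form for each consented participant and section 8 already requires the reason for stopping. The downside for the sponsor is that the reported success proportion may be lower.
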